records, as well as from patient reports of health service use; data will be collected at months 6, 12, and 18. We will obtain and abstract medical records guided by the information in the summary document (see Health Services Use Summary included as a supplemental study document) and from the patient using provided tracking tools of providers they have seen, tests they have undergone, etc. (see Tip Sheet in supplemental study documents). Patient-reported outcomes will be collected at baseline, 6, 12, and 18 months primarily via a REDCap form, with telephone, mail, or in-person data collection as a back-up when needed (See Pro Data Collection form in supplemental study documents).

ARM A (SCP document delivered to the patient & Primary Care Provider [PCP]):

Patient participants randomized to Arm A will be sent a copy of the SCP within approximately 3 months of completion of treatment and a copy will be added to their medical record. A copy of the SCP will also be sent to the PCP on record. The SCP will be completed by a nurse, nurse practitioner, or physician assistant. The SCP will be accompanied by a cover letter that will be signed by a member of the clinical team.

ARM B (SCP document provided to the patient in an in-person survivorship visit and copy sent to PCP):

Patient participants randomized to Arm B will receive a copy of the SCP during an in-person ‘stethoscope free’ visit with a nurse, nurse practitioner, or physician assistant. A copy of the SCP will be added to the medical record and a copy will be sent to the primary care provider on record. The visit will be scheduled after consent is signed and will occur within approximately 3 months after treatment completion. The visit will focus on review of the SCP content and offer an opportunity for patients to ask questions about any aspect of the plan or associated treatment and survivorship issues.

ARM C (SCP document provided to the patient in an in-person survivorship visit with an additional follow-up visit and copy of the document sent to PCP):

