Patient participants randomized to Arm C will receive a copy of the SCP during an in-person ‘stethoscope free’ visit with a nurse, nurse practitioner, or physician assistant. A copy of the SCP will be added to the medical record and a copy will be sent to the primary care provider on record. The visit will be scheduled after consent is signed and will occur within approximately 3 months after treatment completion. The initial visit will focus on review of the SCP content and offer an opportunity for patients to ask questions about any aspect of the plan or associated treatment and survivorship issues. In addition, patients randomized to Arm C will receive a follow up survivorship visit approximately 6 months after the initial in-person ‘stethoscope free’ visit. The follow-up visit will focus on a review and refresher of the SCP and offer patients the opportunity to ask about any persistent or emerging issues.

- c. Blinding, including justification for blinding or not blinding the trial, if applicable.

Given the nature of the interventions, it is not possible to blind patients or providers to the randomization arm.

- d. Justification of why participants will not receive routine care or will have current therapy stopped.

All patients will receive routine care and there is no impact on current therapy. This study is evaluating three different approaches for survivorship care planning, each of which is standard of care.

- e. Justification for inclusion of a placebo or non-treatment group.

Because of the Commission on Cancer Accreditation requirement that all cancer patients completing acute treatment receive a survivorship care plan, a no intervention arm is not appropriate. Rather, this study will

evaluate different approaches for conducting survivorship care planning in the simplest way that is still effective in helping survivors receive appropriate follow-up care.

f. Definition of treatment failure or participant removal criteria.

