We will follow participants for 18 months or until cancer recurrence, at which point they would not receive any further survivorship care planning visits, and no additional health service use or patient reported outcomes data would be collected. Treatment failure is not relevant to this study, and we will not remove participants unless they explicitly withdraw consent. Even if patients do not complete the follow-up surveys, we can still collect their health resource use from their medical records (unless they have withdrawn consent).

g. Description of what happens to participants receiving therapy when study ends or if a participant's participation in the study ends prematurely.

Not applicable as no therapy is included in this study.

RECRUITMENT PROCESS: Clinic and study staff trained in research ethics and HIPAA requirements will coordinate identification and recruitment of potential participants. Specifically, potential participants will be identified during chart review in advance of a routine clinic visit or during a routine clinic visit with a provider. The research team will be searching medical records for patients who have completed, or will soon be completing, treatment. Searching for patients with active treatment appointments is one, but not the only, way we may identify eligible patients. The clinical teams have agreed to provide us with insights on the best ways to identify patients potentially eligible for the study based on their medical records. Potential participants will be approached by a member of clinic staff to determine willingness to learn more about a study for which they may be eligible.

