Those members of the research team (principal investigator, co-investigators, study staff) who consent patients have been trained in informed consent procedures, are familiar with the protocol, and are listed as a consenter in the application document. Patients are given adequate time and privacy to consider the research study. Before the patient signs the consent, the consenter must be satisfied that the participant understands the information provided, has had an opportunity to discuss the information and ask questions, and is aware that he/she may withdraw from the study at any time. We will not be enrolling Non-English speaking participants to this study.

STUDY IMPLEMENTATION: We will use stratified randomization to assign enrolled patients 1:1:1 to the 3 study arms using a random number generator with the condition concealed until randomization. Patients and their clinicians will be informed of the condition to which the patient was assigned after randomization. The SCP template will be completed via EPIC or in paper format. The EPIC templates have been developed and created in EPIC with the guidance of the clinical co-investigators and the clinic staff. Currently, we are working with clinic staff to test the EPIC templates and then to work with the EPIC programming team make necessary modifications for staff and patient utility. The SCP that has been built into EPIC is based on the template developed by the American Society of Clinical Oncology (ASCO) via a multi-stakeholder process. This ASCO template has been revised and refined in consultation with the clinical co-investigators and advisors to improve functionality and processes in the clinics involved in the trial (e.g., through drop-down menus) (See supplementary study documents for mock-ups of each of the 3 EPIC templates). A member of the clinical staff (and not research staff) will be in charge of the creation of the SCP. The specific follow-up care recommended will be informed by ASCO and other relevant guidelines, as well as standards of care in each clinic. The general recommendations will be based on the guidelines as outlined in Table 1, but the clinician completing the form can tailor the specific recommendations based on clinical judgement. As described above, the SCP will either sent to the patient (Arm A) or delivered in an in-person visit conducted by a nurse, nurse practitioner, or physician assistant (Arms B & C).

Table 1: Recommended Follow-up Care and Outcome Measures

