DATA ANALYSIS: Comparing the three models of SCPs, we will examine whether there are differences between intervention arms in receipt of care as recommended on the SCP, regardless of whether the SCP was received ('intention to treat'), and also whether receipt of an SCP leads to appropriate care receipt, comparing those who received a SCP to those who did not. In both cases, the endpoint is the proportion of patients who receive all cancer-related follow up care. We will also examine each component of appropriate care individually (e.g., proportion receiving mammogram). Analysis will be by Fisher's exact test for differences between groups. To help quantitatively describe the differences between groups, we will also use binary or categorical logistic regression models as appropriate to estimate odds ratios with 95% confidence intervals. To account for the stratified randomization, we will also include a regression model that estimates the main SCP-type effect while adjusting for cancer type and recruitment site. Planned

subgroup analyses include examining differential outcomes by patient cancer type and recruitment site using interaction analyses. P-values for determining statistical significance of these interaction tests will be corrected for multiple comparisons using a Bonferroni approach.

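### The recipient versus non-recipient comparison in section 7.c is worded causally, but SCP receipt is not randomised, is not defined and has no covariates named for it

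*Combined protocol and SAP*

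**What the plan says.** Section 7.c, Data Analysis, sets out two comparisons on the same endpoint, the proportion of patients who receive all cancer-related follow-up care. The first is by intervention arm, whether or not the SCP was received. The second asks "whether receipt of an SCP leads to appropriate care receipt, comparing those who received a SCP to those who did not". The stated test is Fisher's exact test, supplemented by logistic models where suitable. One model has named covariates, cancer type and recruitment site. It estimates the effect of SCP type and is there to reflect the stratified randomisation.

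On allocation, section 4 (Study Implementation) will "use stratified randomization to assign enrolled patients 1:1:1 to the 3 study arms". Section 4.e explains that, because of an accreditation requirement, "a no intervention arm is not appropriate".

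Delivery differs by arm (section 4.b). For Arm A: "Patient participants randomized to Arm A will be sent a copy of the SCP within approximately 3 months of completion of treatment". For Arm B: "Patient participants randomized to Arm B will receive a copy of the SCP during an in-person" visit. Arm C has the same first visit and a second one about 6 months later. For the chart and the primary care provider (PCP) in Arms B and C: "A copy of the SCP will be added to the medical record and a copy will be sent to the primary care provider". Arm A likewise has a copy filed and one sent to the PCP. Nothing in the text says which of these events makes a patient a recipient, by when, or from what source.

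**The concern.** The second comparison asks a causal question of a variable that the trial does not randomise. No arm is assigned to go without an SCP, so a non-recipient can only be someone for whom the assigned delivery did not happen. That group is selected after randomisation, and two kinds of selection are plausible from the design itself.

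- **Arm.** A posted document and a document handed over at an appointment can fail at different rates, so receipt is partly a proxy for delivery model.
- **Engagement.** If receipt means attending the visit, patients who attend may also be those who keep surveillance appointments. Sections 8.e and 11 add that participants bear out-of-pocket costs such as copays for the Arm B and C visits. Cost could plausibly affect both attendance and follow-up care.

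At stake is the interpretation of one analysis on the primary endpoint. Section 3 calls the evidence on SCP impact sparse and mixed, so a significant result reported as receipt producing appropriate care could be taken as evidence of effectiveness.

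**Working it through.** **1. The plan's own figures.** Table 3 gives power for the randomised three-arm comparison only. Simulating the exact 3×2 test reproduces all 18 rows within 2 percentage points (first row: 79.2% stated, 78.8% computed). The documents give no power, expected receipt rate or expected difference for recipients versus non-recipients.

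**2. What is randomised and what is adjusted.** Randomised: arm. Compared: receipt. Covariates named for the arm effect: cancer type and site. Covariates named for receipt: none.

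**3. Expected spurious difference, base case.** Arm sizes are the Table 2 column sums: 126 / 124 / 125. Everything else is assumed:

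- SCP effect: zero.
- Engaged patients: 70%. Endpoint met by 66% of them and 46% of the others, so 0.7 × 0.66 + 0.3 × 0.46 = 60% overall.
- Receipt at the visit in Arms B and C: 92% if engaged, 70% if not.
- Receipt in Arm A: 98% regardless of engagement.

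Non-receipt in Arms B and C = 0.7 × 0.08 + 0.3 × 0.30 = 0.146.

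Expected non-recipients = 126 × 0.02 + 249 × 0.146 = 2.5 + 36.4 ≈ 39.

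Endpoint rate in Arm B/C non-recipients = (0.056 × 0.66 + 0.090 × 0.46) / 0.146 = 53.7%.

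All non-recipients = (2.52 × 0.600 + 36.35 × 0.537) / 38.87 = 54.1%.

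Recipients = (375 × 0.600 − 21.02) / 336.13 = 60.7%, where 21.02 is the expected number of non-recipients meeting the endpoint.

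Spurious difference = 60.7 − 54.1 = **+6.6 points**.

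**4. How often the tests reject at two-sided 0.05 with no SCP effect** (10,000 simulated trials per setting):

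| Setting | Rejects |
|---|---|
| Base case, Fisher | 11.4% |
| Weaker: endpoint 63% vs 53% | 5.9% |
| Weaker: visit receipt 92% vs 85% | 4.9% |
| Stronger: visit receipt 95% vs 50% | 29.2% |
| Received = sent in all arms, 98% / 90% receipt | 3.0% / 4.0% |
| Base, logistic with arm, cancer type, site | 13.4% |
| Same, plus baseline proxy matching engagement in 80% | 8.7% |
| Same, with a perfect proxy (separate run; Fisher there 10.6%) | 4.9% |

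Adjusting for arm does not help, because almost all non-recipients are in Arms B and C. Within those arms, recipients meet the endpoint in (0.600 − 0.0784) / 0.854 = 61.1%, where 0.0784 = 0.056 × 0.66 + 0.090 × 0.46. The gap there is 61.1 − 53.7 = 7.4 points, wider than the crude 6.6.

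**5. Exact Fisher rejection without an engagement model.** 375 patients, recipients' endpoint rate 30% to 70% (the Arm A range in Table 3), no SCP effect:

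| Gap from confounding | 19 non-recipients | 38 | 75 |
|---|---|---|---|
| 0 points | 3.0–3.8% | 3.7–4.0% | 3.9–4.5% |
| 5 points | 4.7–6.9% | 7.3–8.7% | 10.1–12.3% |
| 10 points | 9.9–14.2% | 18.6–22.3% | 30.8–38.7% |

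With few non-recipients and a gap of 5 points or less, the rate stays close to nominal.

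**The case against.** The best defence is that nothing is decided on this comparison. Section 2 and section 7.a tie the choice of delivery model to the primary endpoint by arm, and section 7.c lists the intention-to-treat comparison first. That stands, and it limits the weight of the point. It does not make the second comparison's causal wording valid. Nor does the descriptive label in section 7.c cover it: that label is given to preventive care, non-recommended care and patient-reported outcomes, whereas this comparison uses the primary endpoint.

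A second defence is that the figures are built on assumptions. They are, and several reasonable settings sit near 5%. The design argument does not depend on them.

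A third is that the protocol elsewhere uses associational language: Aim 1 in section 2 and the Overview in section 4.a both speak of provision being associated with follow-up care. That shows the causal verb to be an isolated departure, but it remains in the analysis section.

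A fourth is that the proposed adjustment achieves little. Section 7.c could be read as extending its cancer type and site model to receipt, but the working shows that such variables do not remove confounding by engagement. The main repair is therefore the label and the definition, with the model secondary.

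Two stronger readings should be resisted. A reader might infer that a patient with no completed SCP cannot be scored, because section 7.a bases the endpoint on the individual's SCP. But Table 1 sets out recommended care by tumour type and is an obvious default standard. Section 7.c also scores care as recommended on the SCP whether or not it was received, which presumes that an SCP exists. Any such gap would affect the arm comparison equally, so it is not a fault peculiar to this one. A reader might also take section 4.f as describing routes to non-receipt. It says that follow-up runs "until cancer recurrence, at which point they would not receive any further survivorship care planning visits", and that "we will not remove participants unless they explicitly withdraw consent". The first concerns later visits and data collection, the second removal from the study. Neither addresses receipt of the initial SCP.

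**Conclusion.** The point holds as a problem of inference and labelling. As written, section 7.c could yield a causal conclusion from a non-randomised contrast with an undefined exposure and no covariates named for it. In the illustration Fisher's test rejects in about 11% of trials with no SCP effect, with a spurious difference of about 6.6 points. The range is about 5% to 29% over weaker and stronger inputs, and the rate is 3% to 4% if receipt means sent in every arm regardless of engagement. That dependence on the meaning of receipt is itself a reason to define it. Every receipt and engagement input is an assumption, so the figures show that the bias is possible and how it behaves, not how large it will be here. The confounding leaves the randomised comparison by arm, and the choice of preferred model, untouched. The change should be made, but the conduct of the trial does not hinge on it.

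**What to change.** In section 7.c, Data Analysis:

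1. Replace the causal verb with *is associated with*, in line with section 2 and section 4.a, and label the receipt comparison exploratory and non-randomised.
2. State that conclusions rest on the comparison by arm only.
3. State which event counts as receipt (for example completed, sent, or handed over at a visit), with its source and time window.
4. Report the receipt comparison from a model adjusted for arm, cancer type, site and prespecified baseline patient characteristics, in place of the unadjusted Fisher test. State that this reduces but does not remove confounding by engagement.
5. Report SCP delivery and visit attendance by arm.

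The cost is a few sentences and a small amount of extra analysis. Sample size and the randomised analysis are unchanged. The trial gives up a causal claim about receipt that this comparison could not have supported.

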The SCP is intended to provide clear instructions as to what screening, surveillance, health maintenance, wellness activities and psychosocial care are necessary going forward, with the goal of promoting appropriate clinical service use, reducing overlaps in care, improving patient and provider communication, and ultimately enhancing quality of life through the survivorship trajectory. Our review of the literature indicated a wide variation in rates of compliance with surveillance recommendations. Previous studies show that patient adherence in the survivorship period is varied, depending on the cancer type and/or the type or procedure or office visit to be completed. For example, colorectal cancer survivors completed recommended follow up care with adherence rates varying from 16.7% (Saloum et al, 2012) to 46.7% to 92.3% (Cooper et al, 2008). Rates for breast cancer patients are generally higher, but also very variable (Cooper et al 2008; Snyder et al, 2009; Grunfeld et al, 2010). Thus, we considered a range of adherence probabilities and varying differences in our analytic plan.

One challenge for the field is that the IOM's recommendation was based on "face validity", rather than scientific evidence. Data as to the impact of SCPs on health care delivery and survivorship outcomes remain quite sparse and findings have been mixed. Moreover, the time and resources required for survivorship care planning present substantial barriers to implementation. Nevertheless, the American College of Surgeons' (ACS) Commission on Cancer is now mandating SCPs for all eligible patients by 2019. As of 2013, only 21% of American College of Surgeons Commission on Cancer member organizations reported having developed SCPs (American College of Surgeons Commission on Cancer, 2016). Thus, research on the simplest, most effective approaches for conducting survivorship care planning is critically needed.

4. Study Procedures

- a. Study design, including the sequence and timing of study procedures (distinguish research procedures from those that are part of routine care).

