- Assessment of Survivor Concerns (ASC): The Assessment of Survivor Concerns is a 5-item questionnaire that assesses two subscales: cancer worry and general health worry. Each item is rated on a 4-point scale from 1=not at all to 4=very much. Subscale scores and an overall score are calculated by summing the relevant items. The ASC was developed by Gotay & Pagano and used in a previous study of survivorship care planning (Gotay, C. C., & Pagano, I. S., 2007; Hershman, D. L., et al., 2013).
- Follow-up Care Use among Survivors (FOCUS)-Information Needs Module: The FOCUS information needs questionnaire asks about the need for information regarding 12 topics (Kent, E. E., et al., 2012) Response options are “no,” “yes,” and “not sure.” It was developed by the National Cancer Institute based on previously published information needs questionnaires (Beckjord, E. B., et al., 2008; Mallinger, et al., 2005; Nelson, et al., 2004). The FOCUS study included an evaluation of the impact of survivorship care plans on information needs.

The PROs will be collecting using REDCap (see supplemental study documents). Patients who do not complete the PROs electronically prior to the health-service use follow-up phone calls will have the opportunity to complete the PROs over the phone, by mail, or in-person.

c. Statistical plan including sample size justification and interim data analysis.

No interim analyses are planned.

SAMPLE SIZE: We will recruit 250 participants through JHMI and 125 participants at PRMC oncology program practices (see Table 2). This weighting of recruitment reflects the difference in the number of patients seen at each site, and the fact that we will be studying three separate clinical settings within a large academic center versus a rural based community cancer program. Based on 2011/2012 cancer registry data from each site, our desired sample size is feasible based on approximately 680 breast, 676 colorectal, and 1310 prostate cancer cases newly seen per year at JHMI, and approximately 187 breast, 96 colorectal, and 206 prostate cancer cases newly seen per year at PRMC. To ensure balanced randomization between the three arms, we will stratify by site (JHMI or PRMC) and by cancer type (breast, prostate, or colorectal).

Table 2: Recruitment by Site

Sites	JHMI N=250			PRMC Oncology Program Practices N=125		
Tumor Groups	Breast (n=100)	Colorectal (n=50)	Prostate (n=100)	Breast (n=50)	Colorectal (n=25)	Prostate (n=50)
Arm A	34	17	33	17	8	17

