Arm B	33	16	34	17	8	16
Arm C	33	17	33	16	9	17
Total	100	50	100	50	25	50

Previous studies show that patient adherence in the survivorship period is varied, depending on the cancer type and/or the particular health service being studied. We considered a range of adherence probabilities and varying differences between them among randomization arms. The operating characteristics of the design are shown in Table 3 below. Simulations (1,000) with varying values of the underlying probability of perfect adherence for each study arm provided the estimates in the table. For each simulation, responses for the primary endpoint were randomly drawn from a binomial distribution and compared between study arms with Fisher's exact test. Estimated power is the proportion of simulations that yielded a two-sided p value ≤ 0.05 . Table 3 shows that the study will have more than 80% power to detect differences ranging of about 5% and higher in the proportion of patients with perfect adherence among study arms. Table 3 also shows the power assuming 20% attrition, and even then, we have 80% power to detect differences of 10%-15% (and in some cases lower).

Table 3: Power Calculations for Primary Outcome

Total Sample Size (A / B / C)	Probability of receipt of outcome			Difference between arms	Estimated Power with Type I error = 5%
	Arm A	Arm B	Arm C		
125 / 125 / 125	30%	39.5%	49%	9.5%, 9.5%	79.2%
		37.5%	52.5%	7.5%, 15%	93.2%
		45%	60%	15%, 15%	99.7%
	50%	55%	70%	5%, 15%	88.1%
		65%	72.5%	15%, 10%	91.7%
		65%	80.0%	15%, 15%	99.7%
	70%	75%	87.5%	5%, 12.5%	91.6%
		77.5%	90%	7.5%, 12.5%	96.8%
		82.5%	92.5%	12.5%, 10%	99.3%
Total Sample	Probability of receipt of			Difference	Estimated

Size (A / B / C)	outcome			between arms	Power with Type I error = 5%
	Arm A	Arm B	Arm C		
100 / 100 / 100	30%	39.5%	49%	9.5%, 9.5%	68.7%
		37.5%	52.5%	7.5%, 15%	84.2%
		45%	60%	15%, 15%	98.8%
	50%	55%	70%	5%, 15%	78.7%
		65%	72.5%	15%, 10%	84.8%
		65%	80.0%	15%, 15%	98.5%
	70%	75%	87.5%	5%, 12.5%	82.2%
		77.5%	90%	7.5%, 12.5%	91.6%
		82.5%	92.5%	12.5%, 10%	97.7%

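### The primary test is an unstratified Fisher test although randomisation is stratified by site and cancer type; putting the already planned adjusted model first could recover a little power

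*Combined protocol and SAP*

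**What the plan says.** **Design.** Section 4 (Study Implementation) states: "We will use stratified randomization to assign enrolled patients 1:1:1 to the 3 study arms using a random number generator". Section 7.c (Sample Size) names the factors: "we will stratify by site (JHMI or PRMC) and by cancer type (breast, prostate, or colorectal". That gives 2 x 3 = 6 strata, and Table 2 plans nearly equal arm counts in each.

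**Endpoint.** Section 7.a makes it dichotomous and says that it will decide which delivery model is preferable. Section 7.c (Data Analysis) treats it as all-or-none: "In both cases, the endpoint is the proportion of patients who receive all cancer-related follow up care".

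**Test.** Data Analysis continues: "Analysis will be by Fisher's exact test for differences between groups". The power simulation used the same test without strata: "responses for the primary endpoint were randomly drawn from a binomial distribution and compared between study arms with Fisher's exact test".

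**Adjustment.** Logistic models are then added to describe the differences, followed by: "To account for the stratified randomization, we will also include a regression model that estimates the main SCP-type effect while adjusting for cancer type". Site is the second covariate in that model. No sentence makes this model the primary test.

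**Are the strata prognostic?** Section 7.c says that "patient adherence in the survivorship period is varied, depending on the cancer type and/or the particular health service being studied". Section 3 says: "Rates for breast cancer patients are generally higher, but also very variable". Table 1 lists different surveillance for each cancer, and section 4 lets the clinician tailor it.

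**The concern.** The plan stratifies on two factors, says that adherence may depend on one of them, and specifies a model that uses both. Yet the test that it names and powers for the primary comparison uses neither. When arms are balanced within strata, variation between strata cannot contribute to chance differences between arms, but a pooled test still counts it as noise. If cancer types differ in all-or-none adherence, the pooled test is then stricter than its nominal 5% and leaves some power unused.

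What is at stake is modest. This endpoint chooses the preferred model of care, and the first Table 3 row has 79.2% power at 125 per arm, so a point or two has some value when it needs no extra patients. It would also help to settle in advance which result decides: with a moderate spread, Fisher and CMH disagreed in about 4 to 5% of simulated trials in the two lowest-power rows.

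**Working it through.** **1. Reproduce Table 3.** Inputs: the Table 3 arm rates, 125 or 100 per arm, two-sided p of at most 0.05. The rejection region of the unstratified three-arm Fisher test was enumerated exactly and weighted by binomial probabilities. All 18 stated powers agree within 2 points. Examples, stated against exact: 79.2% and 79.4% (30/39.5/49); 88.1% and 86.5% (50/55/70); 91.6% and 89.9% (70/75/87.5); at 100 per arm, 68.7% and 69.0% (30/39.5/49). This confirms that the powered test is unstratified and that Table 3 is correct for it.

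**2. Why the pooled test becomes conservative.** From Table 2 the cancer shares are breast 150/375 = 0.4, colorectal 75/375 = 0.2, prostate 150/375 = 0.4. With share w_k and rate p_k for cancer k and overall rate p:

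p(1 - p) = sum of w_k p_k(1 - p_k) + sum of w_k (p_k - p)^2

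The pooled test uses the whole left side. With balanced cells, arm differences vary only through the first (within-cancer) term. Let r be that term divided by p(1 - p). On 2 df the tail probability of x is exp(-x/2), so the true size is approximately 0.05^(1/r).

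- Mild, assumed breast/colorectal/prostate 60/40/50%: p = 0.52; within 0.2440; total 0.2496; r = 0.978; size about 4.7%.
- Moderate, assumed 70/30/50%: p = 0.54; within 0.2260; total 0.2484; r = 0.910; size about 3.7%.

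Simulation gave about 4.7% and 3.7% for Fisher, and about 4.8% for CMH at the moderate spread.

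**3. Power.** 20,000 simulated trials per setting, with the Table 2 cells (126/124/125). The spreads enter as fixed logit offsets by cancer, and each arm's intercept is solved to its own Table 2 mix so that the arm total equals the Table 3 rate. For scale, the moderate spread in the 30% arm means about 44% breast, 12% colorectal and 25% prostate (0.4 x 44 + 0.2 x 12 + 0.4 x 25 = 30).

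Gain of stratified CMH (2 df, six cells) over Fisher, in points:

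| Assumed spread | Rows 30/39.5/49 and 50/55/70 | Other seven rows | All nine rows |
|---|---|---|---|
| None | about 0 | down to -0.5 (70/75/87.5) | -0.5 to +0.1 |
| Mild | 1.3 to 1.7 | 0 to 0.8 | 0 to 1.7 |
| Moderate | 3.7 to 4.7 | 0.1 to 2.4 | 0.1 to 4.7 |

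The largest gains fall in the two rows with the lowest power. Fisher's own power does not fall as the spread grows: in the first row it stays at 79.5 to 80.5%.

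**4. If allocation is not blocked within strata.** The documents do not describe blocking. With simple allocation, Fisher's size was 4.8 to 5.3% for no to moderate spread, so the conservatism disappears. The 2-df likelihood-ratio test for arm (logistic: arm + cancer type + site) against Fisher, rows 30/39.5/49 and 50/55/70:

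- none: 79.9 vs 79.9% and 86.5 vs 86.1%
- mild: 80.3 vs 79.3% and 87.4 vs 86.6%
- moderate: 83.1 vs 79.4% and 89.8 vs 86.7%

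**The case against.** The sponsor can fairly say that nothing here is wrong. The pooled test is valid, it is the test that was powered, and it matches an endpoint stated as a proportion of patients. The stratification is not ignored, since the adjusted model is planned for exactly that reason; only its rank is in question. All of this stands.

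The size of the gain is also open to challenge. The documents give no rate by cancer type for this endpoint. Section 3 reports colorectal rates from 16.7% to 92.3% and calls breast rates very variable, and it gives no prostate figure although prostate is 150 of 375 patients. Table 1 lists different numbers of services per cancer, but that does not prove different all-or-none rates: if receipt of services were fully dependent within a patient, the rates could be equal. This stands too, and it is why the range above starts at zero or slightly below.

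The change has a cost: an exact p-value becomes asymptotic, and Table 2 has only 8 or 9 colorectal patients per arm at PRMC. In simulation the cost was small. The likelihood-ratio test had size of about 5.0 to 5.4%, so a few tenths of a point of its power reflect that. CMH had size close to 5%.

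What the objection does not remove is that the better-matched analysis is already specified and is merely placed second.

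**Conclusion.** The point holds as an optional efficiency gain. The named and powered primary test does not use the stratification factors, and a test that does would gain nothing to about 1.7 points of power under a mild difference between cancers and up to 4.7 points under a moderate one. Both differences are assumptions. The figures also assume a common odds ratio for arm across strata, the Table 2 cell sizes and 125 per arm.

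Four stronger readings are tempting and are not supported:

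- *The primary analysis is invalid or inflates type I error.* It does not; any departure seen with balanced cells is in the conservative direction.
- *Table 3 overstates power.* It reproduces for the test that it describes, and Fisher's power does not drop when cancers differ.
- *A gain of 4 to 5 points can be expected.* That needs the moderate spread and occurs only in the two lowest-power rows. Wider assumed spreads give more, but nothing in the documents supports them.
- *Attrition makes this pressing.* Section 4.f keeps record-based service use for patients who skip surveys, so no such argument is made.

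**What to change.** In section 7.c (Data Analysis), name the stratum-adjusted test as the primary three-arm comparison. The preferred choice is the 2-df likelihood-ratio test for arm from the logistic model already planned (arm + cancer type + site); a CMH general-association test over the six cells is the alternative. Keep Fisher's exact test as supportive. Report the arm proportions and their differences so that the result still reads as a proportion of patients. State also whether allocation is blocked within strata.

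The cost is wording only: no new data, variables or patients. The primary p-value becomes asymptotic. If cancer type and site turn out not to be prognostic, CMH can lose about half a point with the Table 2 cells (up to 0.7 with unblocked allocation). The likelihood-ratio test lost nothing to Fisher in any setting run.
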